### 6.1.2 Secondary Efficacy Endpoints

1. Proportion of subjects developing AKI (any stage) based on SCr criteria from the KDIGO guideline within 7 days after T0 (i.e., until Visit 8) (AKI-SCr7d).

[SCr evaluation visit: baseline, Visit 3, 4, 5, 6, 7 and 8 (24 hours, 48 hours, 72 hours after T0, and Day 5, 6 and 7/DoD). If the hospital discharge is earlier than Day 7, then the visits prior to DoD and Visit 8 (DoD) will be used.]

- If the subject meets at least one of the following conditions, then the subject will be treated as developing AKI-SCr7d.
  - Increasing in SCr  $\geq 0.3 \text{ mg/dL}$  within any 48 hours until Visit 8; and/or,
  - Increasing in SCr  $\geq 1.5$  times baseline until Visit 8.

2. Proportion of subjects developing AKI based on all captured criteria from the KDIGO guideline within 72 hours after T0 (AKI-KDIGO72h).

[SCr evaluation visit: baseline, Visit 3, 4 and 5 (24, 48, 72 hours after T0)]

[UO evaluation visit: Visit 3, 4, and 5 (0-12 hours, 12-24 hours, 0-24 hours, ..., and 48-60 hours, 60-72 hours and 48-72 hours after T0)]

- If the subject meets at least one of the following conditions, then the subject will be treated as developing AKI-KDIGO72h.
  - Increasing in SCr  $\geq 0.3$  mg/dL within any 48 hours until Visit 5;
  - Increasing in SCr  $\geq 1.5$  times baseline until Visit 5; and/or,
  - Urine volume  $< 0.5$  ml/kg per hour for any one of 12 consecutive hours until Visit 5 (i.e., 0-12 hours after T0, 12-24 hours after T0, ..., or 60-72 hours after T0).
- 3. Proportion of subjects developing AKI based on all criteria from the KDIGO guideline within 7 days after T0 (AKI-KDIGO7d).

[SCr evaluation visit: baseline, Visit 3, 4, 5, 6, 7 and 8(24 hours, 48 hours, 72 hours after T0, and Day 5, 6 and 7/DoD). If the hospital discharge is earlier than Day 7, then the visits prior to DoD and Visit 8 (DoD) will be used.]

[UO evaluation visit: Visit 3, 4, 5, 6, 7 and 8 (0-12 hours, 12-24 hours, 0-24 hours, ..., and 120-132 hours, 132-144 hours and 120-144 hours after T0). If the hospital discharge is earlier than Day 7, then the visits prior to DoD and Visit 8 (DoD) will be used.]

  - If the subject meets at least one of the following conditions, then the subject will be treated as developing AKI-KDIGO7d.
    - Increasing in SCr  $\geq 0.3$  mg/dL within any 48 hours until Visit 8;
    - Increasing in SCr  $\geq 1.5$  times baseline until Visit 8; and/or,
    - Urine volume  $< 0.5$  ml/kg per hour for any one of 12 consecutive hours until Visit 8 (i.e., 0-12 hours after T0, 12-24 hours after T0, ..., or 132-144 hours after T0).
- 4. Proportion of subjects with MAKE defined as all-cause mortality, renal replacement therapy (RRT) and/or  $\geq 25\%$  sustained reduction in eGFR based on SCr within 30 days after day of surgery (MAKE30).
  - If the subject meets at least one of the following conditions by day 30 (Visit 9), then the subject will be treated as with MAKE30.
    - All-cause mortality;
    - Initiation of RRT; and/or,
    - eGFR based on SCr at day 30 (Visit 9) equal to or less than 75% of the baseline value.
- 5. Proportion of subjects with MAKE defined as all-cause mortality, RRT and/or  $\geq 25\%$  sustained reduction in eGFR based on SCr within 90 days after day of surgery (MAKE90).
  - If the subject meets at least one of the following conditions by day 90 (Visit 10), then the subject will be treated as with MAKE90.
    - All-cause mortality;
    - Initiation of RRT; and/or,
    - eGFR based on SCr at day 90 (Visit 10) equal to or less than 75% of the baseline value.

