2. During surgery, the following data have to be assessed in the electronic case report form (eCRF): Procedures (coronary artery bypass graft surgery and/or valve surgery, thoracic aortic surgery, extracorporeal membrane oxygenation, use of ventricular assist device, redo cardiac surgery) and duration of CPB; lowest intraoperative mean arterial pressure; perioperative fluid balance and medication (fluid intake, UO, blood products, drain output, blood loss, inotropics/vasopressors and furosemide); time of incision and closing of skin; T0 and perioperative complications.
3. If the subject is discharged from hospital before day 7, visit 8 will be done on the day of discharge and no site visits are required after discharge up to day 7. If discharged after day 7, no additional assessments are required after day 7 up to discharge except for the recording serum creatinine (SCr) from local laboratory testing.
4. At days 30 and 90, only body weight needs to be measured. A full physical examination is not required.
5. Subjects will only be randomized if postoperative NephroCheck® (NC) AKIRisk® score (assessed between 2 to 22 hours after T0) is  $> 0.3$  (ng/mL) $^2/1000$ . If the AKIRisk score is  $\leq 0.3$  (ng/mL) $^2/1000$ , the subject cannot be randomized and will be followed up in the observational arm, see Schedule of Assessments [[Table 2](#)].  
NC measurements at visits 3, 4 and 5 do not have to be performed at sites: urine samples at visits 3, 4 and 5 will be taken, but frozen until later assessment at central lab.
6. Safety central laboratory tests including serum creatinine (SCr) and cystatin C.
7. If the subject is discharged from hospital after day 7, the last result of SCr before discharge from local laboratory testing will be collected.
8. UO assessment: from T0 (visit 2) to T72 (visit 5) when the subject is in the ICU, UO will be recorded every 12 hours and fluid intake will be recorded every 24 hours. The eCRF should indicate when UO data have to be recorded from the subject ICU record. During the first 72 hours following surgery (i.e., visits 3 to 5), the investigator will be asked to record information on AKI-UO stages 1 to 3 in the eCRF to assess their occurrence as per investigator discretion. When the subject is discharged from the ICU, but is still in the hospital UO and fluid intake every 24 hours will be recorded up to day 7 (visit 8).
9. Include albuminuria dipstick.

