**Table 2 Schedule of Assessments – Subjects in the Observational Cohort**

Study Period	Screening	Surgery			Follow-up Period						Unscheduled
		Visit Number	1	2 	3	4	5	8	9 	10/EoS 	
Day	-28	pre	peri 	post	2	3	4	7/DoD	30	90	
Visit Window	≥ -28 days	-	-	-	T0 + 24 hours	T0 + 48 hours	T0 + 72 hours	4 to 7 days	23 to 37 days	83 to 97 days	
Assessment											
Informed Consent	X										
Inclusion/exclusion criteria	X										
Medical history, demographics	X										
Medication use	X	X	X	X	X 						
Physical examination	X 										
Body weight, height	X										
Subject randomization											
Vital signs	X	X									
Hematology, biochemistry	X 	X 			X 	X 	X 	X 	X 	X 	
Urinary output 				X	X	X	X	X			O
Urinalysis	X 	X 						X 	X 	X 	X 
Pregnancy test	X 	X 									
NephroCheck®				X 	X 	X 	X 				
Biomarkers 		X		X	X 	X 	X 				
Assessment of AEs	X	X	X	X	X 						
Assess follow-up parameters											
Assess MAKE parameters					X	X	X	X	X	X	X
APACHE-II 		X		X							
EQ-5D-5L		X									
Blood samples for pharmacokinetics											
Blood samples for pharmacodynamics											
Biobanking sample PGx		X									

AE: adverse event; APACHE-II: acute physiology and chronic health evaluation II; DoD: day of discharge from hospital; EoS: end of study; EQ-5D-5L: 5-level European Quality of Life 5 Dimensions Questionnaire; MAKE: major adverse kidney events; O: if possible; PGx: pharmacogenomics; T0: time point 0; UO: urine output.

1. The preoperative period is defined as the part of the day of surgery before the incision. The peri-operative period is defined as the period between incision and T0 (i.e., the time point when the subject comes off the cardiopulmonary bypass pump [CPB]). The postoperative period is the period after T0.

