2. During surgery, the following data have to be assessed in the electronic case report form (eCRF): Procedures (coronary artery bypass graft surgery and/or valve surgery, thoracic aortic surgery, extracorporeal membrane oxygenation, use of ventricular assist device, redo cardiac surgery) and duration of CPB; lowest intraoperative mean arterial pressure; perioperative fluid balance and medication (fluid intake, UO, blood products, drain output, blood loss, inotropics/vasopressors and furosemide); time of incision and closing of skin; T0 and perioperative complications.
3. Central laboratory tests
4. Additional urine samples will be taken and stored to assess various clinical and compound related biomarkers.
5. APACHE-II score is recorded on visit 2 preoperatively, postoperatively. Results from local laboratory testing can be used, and the result closest to the indicated time points should be recorded.
6. Visit 1 can be close to the day of surgery. If the results from the central laboratory testing of aspartate aminotransferase (AST), alanine aminotransferase (ALT), total bilirubin and eGFR are not yet available at time of randomization, results from local laboratory can be used for verifying randomization requirements if assessed within 7 days before the day of surgery up to initiation of surgery. When the surgery is scheduled within 2 days after screening visit 1 and it is not feasible to perform blood and/or urine samplings at visit 1, the sampling at visit 1 can be by-passed if the results from local laboratory are available for verifying randomization requirements.
7. Presurgery pregnancy test at the day of surgery will be assessed locally with urine dipstick test.
8. AEs and medication use will be collected until 24 hours after T0. However, AEs related to MAKE parameters will be collected until the EoS visit. AEs will be followed up until resolved including medication use for the AE.
9. Local laboratory test results will be collected from medical records, including serum creatinine and serum cystatin C (if available).
10. 24-hour urinary output data will be collected from medical records (if available).
11. Subjects will only be randomized if postoperative NephroCheck® (NC) AKIRisk® score (assessed between 2 to 22 hours after T0) is  $> 0.3 \text{ (ng/mL)}^2/1000$ . If the AKIRisk score is  $\leq 0.3 \text{ (ng/mL)}^2/1000$ , the subject cannot be randomized and will be followed up in the observational arm.

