## **5.6 Prognostic Factor Analysis Set (PFAS)**

The Prognostic Factor Analysis Set (PFAS) consists of NC positive subjects, who are randomized to placebo group, and the NC negative subjects, who are in the observational cohort.

The PFAS will be used for exploring the prognostic factors and comparison with to NC test.

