## 7.9 Other Analyses

### 7.9.1 Analysis for Observational Cohort

[Analysis population: PFAS, Analysis group: Weighted Total (PFAS)]

Potential risk factors (demographics, subject characteristics, biomarkers) for development of AKI and MAKE (AKI-SCr72h, AKI-SCr7d, MAKE30, and MAKE90) will be explored. Population standardization is used in this analysis. Weighted Total (PFAS) is the set of NC negative group and NC positive group weighted by (the number of subjects assigned to Placebo group + the number of subjects assigned to ASP1128 group)/ (the number of subjects in Placebo group). The estimate of the unadjusted risk ratio, 2-sided 90% confidence interval, true positive rate, and true negative rate for AKI and MAKE (AKI-SCr72h, AKI-SCr7d, MAKE30, and MAKE90) proportion will be calculated by risk factors listed in [\[Table 13\]](#). In Analysis for Observational Cohort, subjects whose status of AKI and MAKE is unknown due to, say, the missing data of SCr will not be counted as AKI/MAKE event. This treatment for missing data is different from it for primary and secondary endpoints.

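### In the SAP 7.9.1 NephroCheck comparison, 7-day creatinine AKI is judged on Visits 3 to 8 in NC-positive placebo subjects but on Visits 3, 4, 5 and 8 in NC-negative subjects; this tilts the result towards NephroCheck, by an amount the documents do not fix

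*SAP*

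**What the plan says.** **The endpoint.** SAP 6.1.2 item 1 gives the only derivation of AKI-SCr7d. It uses "SCr evaluation visit: baseline, Visit 3, 4, 5, 6, 7 and 8", with Visit 8 moving to the day of discharge if that comes before day 7. A subject has an event with a rise of at least 0.3 mg/dL "within any 48 hours until Visit 8; and/or" a value at or above 1.5 times baseline.

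**Where it is reused.** SAP 7.9.1 takes AKI-SCr7d as one of four outcomes and plans, for each factor in SAP Table 13: "The estimate of the unadjusted risk ratio, 2-sided 90% confidence interval, true positive rate, and true negative rate for AKI and MAKE". AKIRisk above 0.3 is one of those factors. The population is the Prognostic Factor Analysis Set (PFAS), which SAP 5.6 defines as "NC positive subjects, who are randomized to placebo group, and the NC negative subjects, who are in the observational cohort". In this analysis unknown AKI status counts as no event. No separate visit list is given for it.

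**What is measured.** SAP Table 1 schedules chemistry for randomized subjects at every visit from 3 to 8; footnote 6 reads "Safety central laboratory tests including serum creatinine (SCr) and cystatin C". SAP Table 2 ("Schedule of Assessments – Subjects in the Observational Cohort") has post-surgery columns for Visits 3, 4, 5, 8, 9 and 10 only, and its footnote 9 reads "Local laboratory test results will be collected from medical records, including serum creatinine and serum cystatin C (if available". Protocol 2.2.1 rules out study blood draws in that cohort after Visit 2. Protocol Table 8 gives biochemistry for a range running from Visit 3 to Visit 10, which read literally includes Visits 6 and 7. But Protocol 5.7.4, which introduces that table, ties collection to the Table 2 visits. SAP 7.11.3 analyses by CRF visit and makes no exception for this cohort.

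**The concern.** In the PFAS, AKIRisk above 0.3 and having been randomized are the same split. The NephroCheck (NC) result and the creatinine schedule are therefore fully confounded. An AKI missed in an NC-negative subject turns from a false negative into a true negative, which raises all three measures reported for NC: the risk ratio, the true positive rate and the true negative rate.

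The other Table 13 factors, apart from AKIRisk above 0.7, are not aligned with the schedule by design. Protocol 7.8.2 plans to compare risk factors with the NC test, so that comparison would lean towards NC. At stake is the exploratory objective of finding markers of AKI risk, for which up to 440 observational subjects are followed.

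**Working it through.** The documents give no count of usable creatinine pairs, so there is no figure of theirs to reproduce.

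**1. Times.** Visits 3, 4 and 5 are at 24, 48 and 72 h after T0 (Tables 1 and 2). Continuing daily, Visits 6, 7 and 8 fall at 96, 120 and 144 h. This agrees with the last SAP 6.1.2 urine windows for Visit 8, "120-132 hours, 132-144 hours and 120-144 hours after T0". Place baseline at 0 h for now.

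**2. Pairs no more than 48 h apart, Visit 8 on day 7.**
- Randomized {0, 24, 48, 72, 96, 120, 144}: six 24-h gaps + five 48-h gaps = 11.
- Observational {0, 24, 48, 72, 144}: 0–24, 0–48, 24–48, 24–72, 48–72 = 5. Visit 5 to Visit 8 is 144 − 72 = 72 h, so Visit 8 adds no pair.
- Ending after 72 h: 48–96, 72–96, 72–120, 96–120, 96–144, 120–144 = 6 against 0.

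**3. Baseline timing and discharge day.** SAP section 6 takes baseline before surgery, hence before T0. Timed strictly, the baseline-to-48 h pair exceeds 48 h and drops out of both groups.

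| Visit 8 on | Randomized (ending after 72 h) | Observational (ending after 72 h) | Strict baseline |
|---|---|---|---|
| day 7 | 11 (6) | 5 (0) | 10 v 4 |
| day 6 | 9 (4) | 6 (1) | 8 v 5 |
| day 5 | 7 (2) | 7 (2) | 6 v 6 |
| day 4 | 5 (0) | 5 (0) | 4 v 4 |

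For the 1.5-times test with Visit 8 on day 7, there are 6 post-baseline values against 4.

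**4. Two trajectories (mg/dL, baseline then Visits 3 to 8).**
- 1.20, 1.20, 1.20, 1.25, 1.45, 1.60, 1.60. On the randomized schedule, Visit 5 to Visit 7 gives +0.35 in 48 h: an event. On the observational schedule the same +0.35 spans 72 h and 1.60/1.20 = 1.33: no event.
- 1.00, 1.00, 1.05, 1.10, 1.50, 1.30, 1.15. On the randomized schedule Visit 6 is 1.5 times baseline: an event. On the observational schedule Visit 6 is not seen: no event.

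**5. Size, for illustration.** Let d be the share of NC-negative 7-day events that the full schedule would find and the observational one misses. With no NC association, the expected risk ratio (RR) is 1/(1 − d). For a true association, take 60% AKI in NC-positive subjects (the plan's placebo assumption) and an assumed 20% in NC-negative. SAP 7.9.1 weights the placebo group by (110 + 110)/110 = 2, so 220 weighted against 440 subjects: 132 and 88 true events, and 220 − 132 = 88 NC-positive subjects without an event. Then:
- RR = 0.60/[0.20(1 − d)]
- true positive rate (TPR) = 132/[132 + 88(1 − d)]
- true negative rate (TNR) = [440 − 88(1 − d)]/[440 − 88(1 − d) + 88]

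| d | RR, no association | RR, 60% v 20% | TPR | TNR |
|---|---|---|---|---|
| 0 | 1.00 | 3.00 | 60.0% | 80.0% |
| 5% | 1.05 | 3.16 | 61.2% | 80.2% |
| 10% | 1.11 | 3.33 | 62.5% | 80.4% |
| 20% | 1.25 | 3.75 | 65.2% | 80.8% |

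The documents do not give d. Simulated post-surgery trajectories (assumed median baseline 1.1 mg/dL, median peak rise 30% or 50%, measurement CV 3% or 5%) gave d of 0–1% if no rise starts late, 6–8% if 10% of rises start at 48–120 h, and 11–16% if 20% do. A random walk whose daily changes do not diminish after surgery (daily SD 0.06 to 0.15 mg/dL) gave false risk ratios of 1.4 to 1.7. The answer follows from what is assumed about late rises.

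**6. Check of the remedy.** On the shared visits (baseline, 3, 4, 5, 8) with Visit 8 on day 7, the count is 5 v 5, or 4 v 4 with strict baseline.

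**The case against.** The best case against runs as follows. The gap of six pairs is the largest case, not a fixed property of the cohort: discharge is at the investigator's discretion, Visit 8 may fall on days 4 to 7, and the gap is gone by day-5 discharge. Protocol 1.1 places the injury at one point in time, the end of bypass, so few rises may start late, and with none d is 0–1%. At d of 5–10% the true positive rate moves by 1.2 to 2.5 points, which would hardly change a view of NC. The analysis is descriptive and exploratory. And Table 8 may mean that local Visit 6 and 7 values are collected after all.

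Most of this bears on size, and it stands. It does not remove the imbalance. The protocol itself assumes at least a week in hospital, so day 7 is the plan's own base case. The direction does not depend on d. Table 2 governs Table 8 as the text is written, though the two need reconciling.

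A reader might infer more than the documents support:
- That late AKI is lost only in NC-negative subjects. Placebo subjects discharged before day 7 have no required visit until day 30, so theirs is missed too. The difference is confined to time in hospital after Visit 5.
- That counting unknown status as no event adds to the tilt. The rule applies to both groups. With local values present only where the chart has them, an added tilt is plausible, but the documents report no missingness by group.
- That AKI-SCr72h is a clean substitute. Its scheduled visits are shared, but the central-versus-local difference affects it too.

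**Conclusion.** The point holds for one comparison: AKI-SCr7d by NC result in the PFAS. For subjects in hospital beyond day 5, AKI arising after Visit 5 is less detectable in the NC-negative group, and this favours NC on all three reported measures. The counts rest on scheduled times, Visit 8 at 144 h and Table 2 as the governing schedule. The size of the tilt cannot be derived from the documents, may be small, and every risk ratio or rate above is illustrative.

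It would be wrong to read this as a flaw in the efficacy analysis. Both randomized arms share one schedule, so the treatment comparison on AKI-SCr7d, the primary endpoint, the power and the 2-sided 0.10 level are untouched. MAKE30 and MAKE90 do not use the 48-hour rule. The summary within the observational cohort by NC status up to T0 + 24 h uses one schedule and is also unaffected.

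**What to change.** In SAP 7.9.1, for the PFAS only:
- Derive AKI-SCr7d in both groups from baseline and Visits 3, 4, 5 and 8, using the actual Visit 8 date for the 48-hour rule. Keep the full-schedule endpoint for the randomized comparison.
- Tabulate, by visit and NC group, how many subjects have a creatinine value.
- State as a limitation, for AKI-SCr7d and AKI-SCr72h alike, that one group has central protocol samples and the other has local chart values where they exist.
- Reconcile Protocol Table 8 with Table 2. If local Visit 6 and 7 values are in fact collected, the scheduled imbalance does not arise and the first item is unnecessary.

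The cost is SAP wording and programming, with no new samples. The downside is that Visit 6 and 7 data in the placebo group go unused in this analysis and late AKI is under-counted, but alike in both groups. A small residue remains: on the shared list a subject has 5, 6 or 7 pairs with Visit 8 on day 7, 6 or 5, so a difference in length of stay between NC groups would still matter a little.

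The alternative is to abstract all dated and timed local creatinine values up to day 7 for the observational cohort. That keeps late AKI, but needs more chart work, and clinically driven draws may still be fewer in subjects who are well.
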